#### 2.5.1.1.1 Investigational treatment pattern

The pattern of ranibizumab treatment administrations will be summarized for both treatment arms from baseline to month 12. For a given patient, the pattern of ranibizumab treatments will be identified by a series of numbers or letters as defined below:

- T indicates EoT visit (only for patients who discontinue treatment early but stay in the study)
- S indicates EoS visit

- X indicates an extended interval where no visit was required in the maintenance phase for a patient due to DI with an actual treatment strategy of Dynamic PRN or Treat & Extend
- M indicates that the patient missed the visit
- 0 indicates that a patient attended the scheduled visit at which study treatment was not given
- 1 indicates that a patient attended the scheduled visit at which study treatment was given
- F indicates a follow-up visit after EoT without further treatment

For example, if a patient received injections at baseline, months 1 to 5, 8 and 10, attended the visit at months 6 and 7 but was not treated in the study eye, missed month 9, discontinued prior to month 12, the ranibizumab treatment pattern for that patient would be 111111001M1S.

Investigational treatment patterns will be listed for all patients.

#### 2.5.1.1.2 Re-treatments

The definition of re-treatment is provided in [Section 2.1.1](#).

Descriptive statistics for the number of ranibizumab re-treatments during the maintenance phase and the frequency distribution (number of patients without any re-treatment, number of patients with 1 re-treatment, on up to the maximum number of re-treatments for any one patient) will be presented by treatment arm and total. Re-treatment will only be derived for those patients with a completed initial treatment phase.

The time to first ranibizumab re-treatment (in days) during the maintenance phase will be calculated as the period between the date of the first injection (YES treatment given) in the maintenance phase and the date of the start of the maintenance phase (NO treatment given when the reason is one of the three stability criteria, as defined in [Section 2.1.1](#)) + 1 day.

Note: If a patient had no treatment at month 3, missed month 4 and received treatment at month 5 then we can assume that the duration of each month is 30 days; hence time to re-treatment would be 30 + 1 days.

Kaplan-Meier (KM) curves and descriptive statistics will be provided for time to re-treatment. The main focus of this study is to understand the effect of the two treatments of interest. Therefore, time to first re-treatment during the maintenance phase will be derived for:

1. up to EoT

This means:

- if a patient prematurely discontinues treatment (EoT) but stays in the study longer (EoS > EoT), then only data up to EoT will be used for calculation and censoring
- if a patient prematurely discontinues treatment and the study at the same time, then data up to EoS will be used for calculation and censoring
- if a patient does not discontinue treatment early, then data up to EoS will be used for calculation and censoring

2. up to EoS

In case of no ranibizumab re-treatment, the duration will be censored at EoS.

In addition, time to first re-treatment during the maintenance phase will be derived excluding those patients who discontinue treatment early but stay in the study.

The number and percentage of patients experiencing re-treatments during the maintenance phase, together with defined reason for re-treatments, will be displayed by visit.

In addition, descriptive statistics for duration of TFI will be provided by treatment arm and total. A frequency table for the number of TFIs experienced will also be presented.

The proportion of patients with a TFI during the maintenance phase of at least 3 months will be also be summarized by treatment arm and total.

### **2.5.1.2 Laser Photocoagulation**

Different types of laser treatments and regimes can be applied in addition to study treatment to the patients in both arms:

- Focal
- Grid
- Panretinal
- Focal + Grid
- Panretinal + Focal + Grid
- Other

The number of laser treatments up to month 12 will be presented for both treatment arms by frequency distribution (number of patients with no laser treatments, number of patients with 1 laser treatment, on up to the maximum number of laser treatments for any one patient) and cumulatively. Summaries will be presented separately for the different types of laser treatment (see [Section 2.1.1](#)).

Summary tables with the number and percentage of patients who received laser treatment or not and the reason for laser treatment as stated in eCRF will be given by visit.

By-patient listings for laser photocoagulation will be provided.

### **2.5.2 Prior and concomitant therapies**

The number and percentage of patients taking concomitant therapies will be summarized by PT according to the WHO Drug Reference List dictionary (version 15.3 or higher). Summaries of the following will be presented by treatment arm:

- Prior therapies: therapies received prior to the start of study treatment (therapy end date prior to date of first administration of any study treatment)
- Concomitant therapies: therapies received on/ after the start of study treatment (therapy end date on or after the date of first administration of any study treatment)  
Note: Therapies which started prior to the start of study treatment but continued into the treatment period will be classified as concomitant.

For both, prior and concomitant therapies, summary tables will be presented for ocular therapies (for both eyes in addition to study eye and fellow eye separately) and non-ocular therapies.

Concomitant medications as well as significant non-drug therapies that are prohibited as per protocol and given during the conduct of the study while on study treatment will be provided in separate tables. These patients will be identified using the PD M06 (see [Appendix 5.3](#) for details on this PD) and the prohibited medications and significant non-drug therapies will be identified by the medical advisor during the BDRM.

For those patients who discontinued the investigational study treatment prematurely but remained in the study, summary tables will be presented for concomitant ocular therapies (for both eyes in addition to study eye and fellow eye separately) and non-ocular therapies that were received after the EoT visit.

For handling of missing or incomplete start and end dates, see [Appendix 5.1.2](#) of this document.

By-patient listings for prior and concomitant therapies will be provided.

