5.5.8 Prohibited Treatment

Use of the treatments displayed in Table 5-1 is NOT allowed after the start of study (V1).

Table 5-1 Prohibited treatment

Medication/Procedure	Action to be taken
Concurrent use of any anti-VEGF agents either systemic or in the study eye (only permitted in the fellow eye)	To be recorded as a major protocol deviation
Other (investigational) drugs and interventions of any type suspected to influence outcome, i.e. which might influence the course of the underlying ocular disease or the study treatment results, respectively	To be recorded as major or minor protocol deviation and depending on intervention study drug discontinuation to be considered
Concurrent use of peribulbar or intraocular corticosteroids in study eye	To be recorded as major protocol deviation
Concurrent use of intraocular corticosteroids inserts in study eye	Discontinuation from further study treatment
Vitrectomy of study eye	Discontinuation from further study treatment
Systemic medications known to be toxic to the lens, retina or optic nerve, including Deferoxamine, Chloroquine/ hydroxylchloroquine (Plaquenil), Tamoxifen, Phenothiazines and Ethambutol	To be recorded in the eCRF
Treatment with glitazones or fingolimod when newly started during the study period.	To be recorded in the eCRF

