E22	Ocular conditions in the study eye that require chronic concomitant therapy with topical ocular corticosteroids.	Reportable (medical review)
E23	Stroke less than 4 months prior to screening.	Not reportable
E24	Renal failure requiring dialysis or renal transplant.	Not reportable
E25	Untreated diabetes mellitus.	Not reportable
E26	BP defined as systolic value of greater than 160 mm Hg or diastolic value greater than 100 mm Hg at screening or randomization.	Not reportable
E27	Conditions that require chronic concomitant therapy with systemically administered corticosteroids.	Reportable (medical review)
E28	Current use of Medications known to be toxic to the lens, retina or	Reportable

Deviation ID	Description of Deviation	Exclusion from Analyses
	optic nerve, including Deferoxamine, Chloroquine or hydroxychloroquine, Plaquenil, Tamoxifen, Phenothiazines and Ethambutol.	(medical review)
E29	Use of any systemic anti VEGF drugs within 3 months prior to Screening.e.g. bevacizumab, ziv afibbercept.	Excluded from PP analysis
E30	Known hypersensitivity to fluorescein or ranibizumab or any component thereof or drugs of similar chemical classes.	Not reportable
E31	Disease severity/medical condition/ treatment expected to progress, recur, or change to an extent may bias the assessment of clinical status of patient or special risk to a significant degree.	Reportable (medical review)
D01	MH or AE - Rhegmatogenous retinal detachment or Stage 3 or 4 macular hole in the study eye and no treatment discontinuation.	Excluded from PP analysis (medical review)
D02	MH or AE - Transient ischemic attack or a stroke during the study and no treatment discontinuation	Not reportable
D03	Pregnancy but patient not discontinued from trial.	Excluded from PP analysis
D04	Vitrectomy that did not lead to discontinuation of study treatment.	Excluded from PP analysis
S01	Patient received Ranibizumab from another study or as commercially available Lucentis	Not reportable
S02	Study task injection of ranibizumab was performed by untrained site personnel.	Not reportable
S03	Patient received study medication which was outside the allowed temperature range and should have not been used any more according to guidelines or QP decision.	Reportable (medical review)
M01	Concurrent use of any anti-VEGF agents either systemic or in the study eye (only permitted in the fellow eye).	Excluded from PP analysis

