M02	Concurrent use of peribulbar or intraocular corticosteroids in study eye.	Excluded from PP analysis
M03	Concurrent use of intraocular corticosteroids inserts in study eye.	Excluded from PP analysis
M04	Systemic medications known to be toxic to the lens, retina or optic nerve, including Deferoxamine, Chloroquine or hydroxychloroquine, Tamoxifen, Phenothiazines and Ethambutol.	Reportable (medical review)
M05	Treatment with glitazones or fingolimod when newly started during the study.	Reportable (medical review)
M06	Other investigational drugs and interventions of any type.	Excluded from PP analysis
O02	Missing FLA assessment at visit 1 for both eyes.	Not reportable
O03	Missing FLA assessment at visit 14 for both eyes.	Not reportable
O04a	Missing FP assessment at visit 1 for both eyes.	Not reportable
O04b	Missing FP assessment at EOS visit for both eyes.	Not reportable

Deviation ID	Description of Deviation	Exclusion from Analyses
O05	Missing BCVA in study eye at any visit.	Not reportable
O06	Missing BCVA in fellow eye at any Screening, EOS and EOT visits.	Not reportable
O07	Missing OCT assessment in study eye at any visit.	Not reportable
O08	Missing OCT assessment in fellow eye at Screening, EOS and EOT visits.	Not reportable
O09a	Intraocular Pressure was not measured prior treatment for study eye.	Not reportable
O09b	Intraocular Pressure was not measured after treatment for study eye.	Not reportable
O10	Inadequate training of Investigators during study conduct.	Not reportable
O12	Screening not 28 to 3 days before Baseline.	Not reportable
O14	End of Study Visit not after last treatment of study medication.	Not reportable
O15	Focal or grid laser photocoagulation done prior 3 months after baseline.	Reportable (medical review)
O16	Any Treatment cycle (PRP) was not completed within 6 weeks	Reportable (medical review)
O17	Panretinal Photocoagulation at baseline or at least within 3 months after randomization in both arms for study eye for respective patients	Reportable (medical review)
O19	PDR laser spots smaller than 500 micro meter for respective patients	Not reportable
O20	Less than 12 weeks between PRP-treatments for respective patients	Not reportable
O21	VA examination done by non-certified personnel for both eyes or study eye only.	Not reportable
O22	OCT examination done by personnel not certified for study.	Not reportable
O23	OCT examination done with a device not registered for study.	Not reportable

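### The tables of prohibited therapies select patients by deviation code M06 alone, so patients whose only prohibited treatment is coded M01 to M05, or who had a study-eye vitrectomy, are left out of them

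*SAP*

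**What the plan says.** SAP 2.5.2 (Prior and concomitant therapies) gives the scope of the extra tables as "Concomitant medications as well as significant non-drug therapies that are prohibited as per protocol and given during the conduct of the study", restricted to time on study treatment. It then sets two steps. The patients come first: "These patients will be identified using the PD M06", with a pointer to Appendix 5.3. The treatments come second: "the prohibited medications and significant non-drug therapies will be identified by the medical advisor during the BDRM".

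Protocol 5.5.8 defines what is prohibited. Its Table 5-1 lists seven kinds of treatment that are not allowed once the study has started at visit 1.

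SAP Table 5-4 (Appendix 5.3) gives these treatments separate deviation codes. M02, for example, is "Concurrent use of peribulbar or intraocular corticosteroids in study eye" and M03 is "Concurrent use of intraocular corticosteroids inserts in study eye". M06, the last of the M series, reads "Other investigational drugs and interventions of any type".

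**The concern.** The scope of the tables and the filter that fills them do not match. The scope is everything the protocol prohibits, while the filter is one code for whatever the other codes do not name. Programmed as written, the tables would carry a title about prohibited therapy and hold only part of it. A reader would have no reason to suspect this, because nothing in SAP 2.5.2 limits the scope to the residual class.

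The content matters in this trial. Patients and physicians know the regimen (protocol 3.2), so use of prohibited treatment could differ between arms. The FAS keeps all data whatever the deviations (SAP 2.2), so BCVA recorded after such treatment can enter the primary analysis. A table of which prohibited treatments were given, by arm, helps the reader judge that.

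**Working it through.** No sample size, power or alpha figure bears on this point, and the plan states no figure to reproduce. The check is to map each row of protocol Table 5-1 to its code in SAP Table 5-4 and ask whether the filter in SAP 2.5.2 selects it.

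| Protocol Table 5-1 row | Code in SAP Table 5-4 | Consequence in Table 5-4 | Selected by M06? |
|---|---|---|---|
| Anti-VEGF, systemic or study eye | M01 | Out of the PPS | No |
| Other (investigational) drugs and interventions | M06 | Out of the PPS | Yes |
| Peribulbar or intraocular corticosteroid, study eye | M02 | Out of the PPS | No |
| Corticosteroid insert, study eye | M03 | Out of the PPS | No |
| Vitrectomy, study eye | D04, in part only | Out of the PPS | No |
| Systemic drugs toxic to lens, retina or optic nerve | M04 | Reportable, medical review | No |
| Glitazone or fingolimod newly started | M05 | Reportable, medical review | No |

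**Coverage as written.** M06 is 1 of 6 M codes and matches 1 of 7 rows. Five rows (M01 to M05) are missed, and vitrectomy is a sixth: 7 − 1 = 6.

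**Can M06 be an umbrella for the M series?** No. M06 removes a patient from the PPS, whereas M04 and M05 are only reportable after medical review. If M06 contained them, every M04 or M05 patient would leave the PPS, and their own entries in Table 5-4 would be pointless. The SAP already has a name for the whole group: in 2.4.2, category M is the class for excluded concomitant medication. SAP 2.5.2 cites a single code within that class.

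**Does the medical-advisor step repair the selection?** Not as written. It decides which therapies count as prohibited; the patients have already been picked by M06. A patient with M06 and a second code is selected, so the gap concerns patients without M06. One by-product is that the same anti-VEGF injection could appear for a patient who also has M06 and be absent for one who does not.

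**Does D04 supply the vitrectomy row?** Only partly. D04 is limited to vitrectomy that did not lead to discontinuation of study treatment, and it names no eye. Table 5-1 concerns the study eye and lists discontinuation as the action. A study-eye vitrectomy followed by discontinuation therefore falls outside D04, and a fellow-eye vitrectomy could fall inside it on a literal reading.

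**Coverage after a change.** Selecting on M01 to M06 gives 6 of 7 rows. A flag for study-eye vitrectomy that does not depend on the deviation code gives 7 of 7.

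**The case against.** The best defence is that little is lost.

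- SAP 2.4.2 requires the number and percentage of patients with each deviation, by arm and in total, and a listing with date, study day, code and severity. M01 to M05 and D04 each get their own rate there.
- SAP 2.5.2 itself requires concomitant-therapy tables by preferred term and arm, with the study eye shown separately, and by-patient listings. Patients with an incident leading to vitrectomy also have their own subgroup outputs (SAP 2.2.1 and 2.6.4).
- PPS membership follows Table 5-4 whatever filter these tables use, and the SAP calls all analyses exploratory.

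All of this stands, and it sets the size of the point.

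A second defence is that M06 was chosen on purpose: codes M01 to M05 already name the drug class, while the content of M06 is unknown until someone reviews it. That is plausible, but it is inference. The SAP does not say so, and the announced scope is all prohibited therapy. A third is that deviation definitions may still change, since SAP 2.4.2 leaves the final list to the blind data review meeting. That limits certainty about what will be produced; it does not correct the rule on the page.

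Three stronger readings are tempting and should not be drawn:

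- *The report would give the wrong rate of contaminating therapy by arm.* It would not, because the deviation summary gives each rate.
- *The omitted treatments are those most able to change BCVA.* The documents do not rank them so. Table 5-1 attaches its wording about influence on outcome to the row that M06 covers. It is true that M01 to M03 lead to PPS exclusion, but so does M06.
- *Six of seven means that most affected patients are missed.* The count is of categories, not of patients.

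**Conclusion.** The selection rule in SAP 2.5.2 is wrong as written, because it cannot deliver the tables that the same paragraph announces. It reaches 1 of 6 M codes and 1 of 7 rows of protocol Table 5-1. The number of patients affected is unknown and could be zero.

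This is a reporting defect in one set of supplementary tables. The primary ANCOVA, the PPS and the deviation rates by arm do not depend on it. It is still worth correcting, because the deviation summary counts patients by code and the general therapy tables mix prohibited with permitted treatment. Only the dedicated tables are meant to show which prohibited treatments were given, and a reader will take them as complete.

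The conclusion assumes that the codes are used as Table 5-4 defines them. In particular, it assumes that a treatment with its own code is not also entered under M06, and that a study-eye vitrectomy, which has its own row in Table 5-1, is not coded there as another intervention. The data review plan and data handling plan, which might say otherwise, are not among the documents.

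**What to change.** In SAP 2.5.2, replace the reference to PD M06 with: *any of PDs M01 to M06, or a study-eye vitrectomy or other Table 5-1 treatment flagged by the medical advisor at the BDRM irrespective of deviation code*. Present the tables by code, so that each class of prohibited treatment can be read by arm and reconciled with the deviation summary.

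Do not rely on adding D04 alone to capture vitrectomy, for the reasons given above. If the sponsor did intend these tables for the residual class only, the alternative is to keep M06 and retitle them accordingly, with a pointer to the outputs that hold the rest.

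The cost is one phrase in the SAP and one filter in the table program. No new data are needed, and the change can be made before database lock.

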## 2.6 Analysis of the primary objective

The primary objective is to demonstrate that the mean average change of BCVA, averaged over all post-baseline visits to month 12, in patients with DME treated with ranibizumab injections at the discretion of the investigator (DI) and in accordance with disease activity criteria is non-inferior to current standard of care (PRN).

The main focus of this study is to understand the effect of the two treatments of interest. Therefore, data from baseline to EoT will be used for primary objective analyses, unless specified otherwise. This means:

- if a patient prematurely discontinues treatment (EoT) but stays in the study longer (EoS is after EoT), then only data up to EoT will be used
- if a patient prematurely discontinues treatment and the study at the same time, then data up to EoS will be used
- if a patient does not discontinue treatment early, then data up to EoS will be used.

In the cases where patients discontinued study treatment early but continued in the study, further sensitivity analysis using any BCVA data collected after treatment ended until the patient completed the study will be presented as defined in [Section 2.6.4](#).

Only the study eye will be evaluated for efficacy.

### 2.6.1 Primary endpoint

The primary efficacy variable of this study is the mean average change from baseline in BCVA over the 12-month treatment period. This is defined as the difference between the average level of BCVA (ETDRS letters) over all post-baseline assessments from month 1 to month 12 (or premature discontinuation if earlier) and the baseline level of BCVA. Average change from baseline in BCVA will henceforth be referred to as visit-averaged change from

baseline in BCVA. Therefore the primary efficacy variable of this study is the mean visit-averaged change from baseline in BCVA from month 1 to EoT.

That is, if BCVA0, BCVA1, BCVA2, ⋯, and BCVA12 define BCVA measurements at baseline, month 1, month 2, ⋯, and month 12, respectively, then the primary efficacy variable D0 is derived as:

$$D0 = [(BCVA1 + BCVA2 + \dots + BCVA12)/12] - BCVA0$$

The primary analysis will be performed after all patients have completed the month 12 visit (or discontinued the study prematurely before month 12) using the FAS based on the Last Observation Carried Forward (LOCF).

## 2.6.2 Statistical hypothesis, model, and method of analysis

As a consequence of the early recruitment termination, all analyses will be interpreted in a purely descriptive manner. Nevertheless, the planned non-inferiority hypothesis testing of the ranibizumab injections at the discretion of the investigator (DI) and ranibizumab injections of current standard care (PRN) for patients with DME will still be performed.

The following hypotheses related to non-inferiority at a one-sided 0.025 significance level will be performed:

Null hypothesis:  $H_0: \mu_{DI} - \mu_{PRN} \leq -\Delta$

Alternative hypothesis:  $H_A: \mu_{DI} - \mu_{PRN} > -\Delta$

where  $\mu_{DI}$  and  $\mu_{PRN}$  are the unknown mean visit-averaged change from baseline in BCVA from month 1 to EoT, in the DI regimen and the PRN regimen, respectively.  $\Delta$  is the non-inferiority margin and is predefined to be 4 letters. The hypothesis testing with respect to non-inferiority of BCVA will be carried out using an analysis of covariance (ANCOVA) model including study treatment (DI, PRN) and center as factors and baseline BCVA as continuous covariate.

The Least Square (LS) (“adjusted”) means for each treatment arm and estimates of the difference (DI - PRN) will be given along with the respective two-sided, 95% CI and the p-value for the (unshifted) null hypothesis ( $\mu_{DI} - \mu_{PRN} = 0$ ).

The one-sided non-inferiority p-value for the shifted hypothesis ( $\mu_{DI} - \mu_{PRN} \leq -\Delta$ ) will be calculated. Non-inferiority will be claimed, if the lower limit of the two-sided 95% CI (equivalent to the one-sided 97.5% CI) does not exceed  $-\Delta$  (i.e. -4 letters).

There are no multiplicity issues as there is only one primary comparison.

The key assumptions that underlie the use of ANCOVA model for the primary analysis will be checked. The normality assumption of the error term will be performed and in case of clear deviations, a non-parametric comparison – Wilcoxon Rank Sum Test – will be performed instead of ANCOVA for the primary analyses. Homogeneity of variance between/ among treatment arms will be evaluated visually.

At each visit, descriptive statistics will be provided for the following values of the primary efficacy variable BCVA by visits and treatment arms:

- Baseline
- Absolute and change from baseline
- Visit-averaged change from baseline in BCVA from month 1 to EoT

Moreover, the course over time for the absolute values and for changes from baseline for BCVA variable will be presented graphically for both treatment arms, showing the mean and SD of the mean per visit.

Individual BCVA level profiles will be listed.

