	
defined to be 4 letters.
 
The hypothesis testing with respect to non-inferiority of BCVA will be carried out using an analysis of covariance model including treatment group and center as factor and baseline BCVA as continuous covariate. For the treatment contrast, the point-estimate will be given with its (two-sided, 95%-) confidence interval and the p-value for the (unshifted) null hypothesis $\mu_{DI} - \mu_{PRN} = 0$. The one-sided non-inferiority-p-value for the shifted hypothesis $\mu_{DI} - \mu_{PRN} \leq -\Delta$ will be calculated additionally. Non-inferiority will be claimed, if the lower limit of the confidence interval does not exceed $-\Delta$.

Key words	Ranibizumab, diabetic macular edema, discretion of the investigator regimen

1 Introduction

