9.4.4 Supportive analyses

The primary analysis will be repeated for the PPS using the same model as the one used for the primary analysis.

The change from baseline in BCVA will be compared between the two treatments based on the assumption of a “Missing at Random (MAR)” process, i.e. assuming that the statistical behavior of a patient who drops out post-withdrawal is the same as that for a patient remaining in the study and sharing the same covariates and the same measurement history.

Gender subgroup analysis will be done for primary objective and key secondary objectives.

[REDACTED]
[REDACTED]
[REDACTED] and [REDACTED]

[REDACTED]

[REDACTED]

In case of significant outliers or deviations from normality assumptions, a nonparametric comparison (Wilcoxon Test) may be performed additionally to the primary analyses.

Further details about the models and analyses will be given in the statistical analysis plan. Any major discrepancies in the results across analyses will be investigated as needed.

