## 4 Change to protocol specified analyses

No change from protocol specified analysis was made.

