#### SAS code for ANCOVA analysis

ANCOVA model will contain ‘treatment’ and ‘center’ as categorical variables, and ‘baseline BCVA’ as continuous. For secondary analysis additional linear covariates might be included, such as ‘HbA1c’, ‘Blood pressure (systolic, diastolic)’, or ‘Lipid levels (cholesterol, HDL-cholesterol, LDL-cholesterol, triglycerides)’.

For the appropriate treatment difference, the treatment arms should be sorted or coded appropriately before using this model.

The ANCOVA analysis will be performed using SAS procedure PROC MIXED as below. Note that for this illustrative example:

- the data are stored in the file data\_set
- treatmentvar = treatment variable

- responsevar = dependent variable
- stratavar = stratification variable
- bsl = baseline value of the responsevar
- alpha = significance level (i.e. 0.05 produces two-sided 95% CI)
- control = control arm (Ranibizumab 0.5 mg in PRN treatment regime)

```
PROC MIXED DATA = <data_set>;
CLASS <stratavar> <treatmentvar>;
MODEL <responsevar> = <stratavar> <treatmentvar> <bsl>;
LSMEANS <treatmentvar> / PDIFF = all CL alpha = <alpha> OM;
RUN;
```

To get the one-sided p-value for the non-inferiority test (margin = 4): add -4 letters to control group and re-run the above code with alpha=0.025 and PDIFF=controlu('<control>').

To get the one-sided p-value for the superiority test (if applicable): re-run the above code with alpha=0.025 and PDIFF=controlu('<control>').

---

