### SAS code for Wilcoxon rank sum test

Wilcoxon Rank Sum Test will be presented as a nonparametric comparison additionally to the primary analyses.

For the appropriate treatment difference, the treatment arms should be sorted or coded appropriately before using this model.

Wilcoxon Rank Sum Test will be presented as a non-parametric comparison additionally to the primary analyses.

- the data are stored in the file data\_set
- treatmentvar = treatment variable
- responsevar = dependent variable
- alpha = significance level

```
PROC NPAR1WAY DATA = <data_set> HL alpha = <alpha>;
CLASS <treatmentvar>;
VAR <responsevar>;
RUN;
```

=====

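### The non-inferiority claim sentence is reversed if read literally, and SAP 2.6.2 lets a data-triggered Wilcoxon test replace the primary ANCOVA where the protocol allows it only as an addition

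*SAP*

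**What the plan says.** **Decision rule.** SAP 2.6.2 sets H0: DI - PRN ≤ -4 against HA: DI - PRN > -4 letters at one-sided 0.025. It then states: "Non-inferiority will be claimed, if the lower limit of the two-sided 95% CI (equivalent to the one-sided 97.5% CI) does not exceed" -4 letters. The protocol synopsis (Data analysis) and protocol 9.4.2 carry the same rule: "Non-inferiority will be claimed, if the lower limit of the confidence interval does not exceed" the negative margin. For the shifted p-value, the ANCOVA code in SAP 5.2.1 instructs the programmer to "add -4 letters to control group and re-run the above code with alpha=0.025 and PDIFF=controlu", which is an upper-tail comparison against PRN.

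**Wilcoxon test.** SAP 2.6.2 says that if the errors clearly deviate from normality, a Wilcoxon rank sum test "will be performed instead of ANCOVA for the primary analyses". Protocol 9.4.4 says that in such a case "a nonparametric comparison (Wilcoxon Test) may be performed additionally to the primary analyses". SAP 5.2.1 agrees with the protocol: "Wilcoxon Rank Sum Test will be presented as a nonparametric comparison additionally to the primary analyses". Its code is "PROC NPAR1WAY DATA = <data_set> HL alpha = <alpha>", with treatment as the only class variable. SAP section 4 declares: "No change from protocol specified analysis was made".

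**The concern.** The claim sentence is the only place where the plan says when non-inferiority is concluded, and its literal meaning is the opposite of HA. A report that applied it literally would give one verdict from the confidence interval and the reverse from the shifted p-value beside it.

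The Wilcoxon sentence raises a different problem. It lets the data decide which test is primary, on a trigger (clear deviations) that has no test or threshold. The replacement test drops the pre-specified center and baseline BCVA terms. As coded, it does not address the 4-letter margin. This departs from the protocol and from the SAP's own appendix, and the SAP's section on changes does not declare it.

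**Working it through.** **Inputs.** Margin 4 letters, one-sided alpha 0.025, SD 10, true difference 0, unstratified t-test, 133 per arm for 90% power (protocol 9.7, SAP section 3). 135 patients randomized 1:1 (SAP 1.1). Range: 120-150 patients (protocol 9.7) and SD 7.5-10, where 7.5 is the middle of the 7-8 letters quoted from RESTORE.

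**1. The plan's own figure.** At 133 per arm, SE = 10 × √(2/133) = 1.226 and the noncentrality is 4/1.226 = 3.262. With 264 df, P(lower limit > -4) = 0.901. The planned 90% is reproduced, but only with the limit required to lie *above* -4. The literal rule would have 1 - 0.901 = 0.099.

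**2. Cut-off at 135 patients.** SE = 10 × √(4/135) = 1.721. Half-width = t(0.975; 133 df) × SE = 1.978 × 1.721 = 3.40. The lower limit is above -4 when the estimate of DI - PRN is above -4 + 3.40 = -0.60. Read literally, the sentence claims non-inferiority at -0.60 or below.

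**3. Claim rates (noncentral t, 133 df).** The literal rate is 1 minus the intended rate.

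| True DI - PRN | Intended rule (limit > -4) | Literal rule (limit ≤ -4) |
|---|---|---|
| -4 | 0.025 | 0.975 |
| -2 | 0.210 | 0.790 |
| 0 | 0.636 | 0.364 |

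Spending about 30 df on centers (103 df) changes 0.636 to 0.634. At a true difference of 0 and over the stated range, the intended rule runs from 58% (N = 120, SD 10) to 90% (N = 150, SD 7.5), and the literal rule from 42% to 10%.

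**4. Direction of the code.** Adding -4 to the PRN values and testing DI greater than PRN is a test of DI - (PRN - 4) > 0, that is DI - PRN > -4. This agrees with HA and is the exact complement of the literal sentence.

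**5. Wilcoxon passages side by side.**

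| Place | Role of the Wilcoxon test |
|---|---|
| Protocol 9.4.4 | Optional addition |
| SAP 2.6.2 | Replaces the ANCOVA |
| SAP 5.2.1 (Wilcoxon code) | Addition, stated twice |
| SAP section 4 | No change from the protocol |

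The ANCOVA and MMRM code blocks each carry the -4 shift instruction; the Wilcoxon block does not. The HL option would produce a location-shift interval, but nothing in the plan compares it with -4. SAP 2.6.4 promises a shifted p-value for supportive and sensitivity analyses, which covers an added Wilcoxon test but not one that has become the primary test.

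**6. What the replacement would do.** Simulation: 67 and 68 patients, normal data, SD 10, no center effect, 3000 runs per setting. The baseline-outcome correlation is an assumption (0, 0.3, 0.5).

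| Test | Claims at 0 | Claims at -4 |
|---|---|---|
| ANCOVA, lower limit > -4 | 64%, 68%, 77% | 2.2-2.7% |
| Wilcoxon shifted by 4, no covariates | 61%, 62%, 62% | 2.1-2.5% |
| Wilcoxon as coded, two-sided p < 0.05 | 4-5% | 60-63% |

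The last row counts rejections of equality, not non-inferiority claims: without the shift, the test mostly signals when DI is worse.

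**7. Hodges-Lehmann limit as support.** In 4000 simulated trials (68 and 67 patients, SD 10, no covariates), the lower 95% Hodges-Lehmann limit exceeds -4 in 2.7% (normal) and 2.5% (t with 3 df, an assumption) at a true difference of -4, and in 62% and 88% at 0. The level is kept.

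**The case against.** The intended direction is not in doubt. H0 and HA stand just before the sentence, the shifted p-value and code point the right way, and the phrase can be read loosely as not going beyond the margin. No code implements a claim at or below -4, so the literal claim rates describe a reading that nobody is likely to apply. All of this stands. It makes the first part a wording error, not a wrong test. It does not make the sentence right, and the sentence appears three times.

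Results are declared purely descriptive. This also stands, and it limits the consequence. But SAP 2.1 and 2.6.2 keep the hypothesis test, and 2.6.2 keeps the claim sentence.

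On the Wilcoxon, Table 5-3 lists only ANCOVA and MMRM for the primary variable. The MMRM and the covariate-extended ANCOVAs in SAP 2.8.2 would still give adjusted comparisons after a switch. SAP 2.6.4 asks for an estimate with a 95% interval for every analysis, and 2.6.2 calls for a shifted p-value under the primary objective. The missing shift line may therefore be an incomplete template, and the 4-letter margin would not vanish from the report. These points show that the replacement rule is the outlier within the SAP. None of them cancels it, and none says how a Wilcoxon primary test would be judged against -4.

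**Conclusion.** Both points hold as written and should be fixed before database lock. The claim sentence contradicts the plan's own hypotheses, code and power. With 135 patients and SD 10, following it literally would turn a 2.5% error rate at the margin into 97.5%. The figures assume a two-sample t comparison with normal data; the df spent on centers hardly matter, and the reversal itself does not depend on SD or sample size.

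The Wilcoxon rule is an undeclared departure from the protocol and contradicts SAP 5.2.1. It removes center and baseline BCVA and, as coded, tests equality. The power cost of losing baseline depends on the assumed correlation: about 3 points at 0 and 15 points at 0.5. The descriptive status of the results tempers both points.

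A minor related error: protocol 9.4.2 equates the lower limit of the two-sided 95% interval with a one-sided 90% limit. The correct figure is 97.5%, as the SAP says. The remark sets no decision limit.

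**What to change.** **SAP 2.6.2, decision sentence.** Replace with: *Non-inferiority is concluded if the lower limit of the two-sided 95% CI (one-sided 97.5%) for DI - PRN is greater than -4 letters.*

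**SAP 2.6.2, Wilcoxon.** State that the test is done in addition to the ANCOVA, which remains the primary analysis whatever the residuals look like. SAP section 4 can then stand on this point.

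**SAP 5.2.1, Wilcoxon code.** Add that the lower 95% Hodges-Lehmann limit for DI - PRN is compared with -4 as support, with alpha set to 0.05 and the arms ordered so that the shift is DI minus PRN.

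**Protocol.** Correct the decision sentence in the synopsis and 9.4.2, and the one-sided 90% remark, at the next amendment.

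**Cost.** SAP wording only, before database lock and unmasking. No new data are needed, and no programming beyond reading a limit that the HL option already produces. Protocol 11.1 requires a written amendment for the protocol sentences, so these can wait for the next one.
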